11.1.9. Serious Adverse Events

A serious adverse event (SAE) is defined as any AE that meets 1 or more of the following criteria:

- The event results in death.
- The event is life-threatening.
- The event is permanently disabling (incapacitating or interfering with the ability to resume usual life patterns).
- The event results in unplanned inpatient hospitalization or prolongation of existing hospitalization.
- The event is a congenital anomaly.
- The event requires medical intervention of any kind in order to prevent any of the aforementioned outcomes.

A serious AE is not necessarily severe; for example, an overnight hospitalization for a diagnostic procedure must be reported as a serious AE even though the occurrence is not medically serious. By the same token, a severe AE is not necessarily serious: for example, nausea of several hours' duration may be rated as severe but may not be considered serious.

An SAE occurring during the study or within 4 weeks of stopping the treatment must be reported to the [REDACTED] and will be communicated to the Sponsor. **Any such SAE due to any cause, whether or not related to the study medication, must be reported within**

24 hours of occurrence or when the investigator becomes aware of the event. Notification can be made using the following fax or email address for the [REDACTED]:

[REDACTED]

The event must also be recorded on the standard AE eCRF. Preliminary reports of SAEs must be followed by detailed descriptions later on, including clear and anonymized photocopies of hospital case reports, consultant reports, autopsy reports, and other documents when requested and applicable. SAE reports must be made whether or not the investigator considers the event to be related to the investigational drug.

Appropriate remedial measures should be taken to treat the SAE, and the response should be recorded. Clinical, laboratory, and diagnostic measures should be employed as needed in order to determine the etiology of the problem. The investigator must report all additional follow-up evaluations to the [REDACTED] within 10 calendar days. All SAEs will be followed until the investigator and Sponsor agree the event is satisfactorily resolved.

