	
 • Patients with chronic obstructive pulmonary disease (COPD), asthma, or other chronic respiratory disease within the last 5 years. • Patients with any contraindication to performing routine spirometry or who are unable to perform a spirometry maneuver (see Appendix 20 for a list of contraindications). • Patients with a current history of symptomatic orthostatic hypotension despite adequate treatment. • Patients with any condition that in the investigator’s opinion would make patients unsuitable or interfere with their participation in the study. Potential issues of concern should be raised to the medical monitor during eligibility review. • Patients who have any clinically significant abnormality or finding from examination, tests, or history that may compromise patient safety. • Patients who have been treated with an investigational drug within 4 weeks or 5 half-lives (whichever is longer) prior to the beginning of the screening period (this includes investigational formulations of marketed products). • Prior exposure to CVT-301.
Planned Sample Size:	Approximately 250 CVT-301 treatment patients and 115 control patients will be enrolled in this study. It is assumed that the drop-out rate will be approximately 25%.
Investigational Therapy (for the CVT-301 treatment group):	
CVT-301 (levodopa inhalation powder [LIP]) Each dose will be administered using 2 sequential inhalations of CVT-301-filled capsules. CVT-301 capsules will be delivered using the CVT-301 inhalers. [REDACTED]
 
[REDACTED] The capsules provided to the CVT-301 treatment group (target nominal respirable dose of approximately 50 mg LD FPD) will deliver approximately 25 mg LD FPD to the lung per capsule inhalation.

Reference Therapy:	There will be no reference therapy or placebo. Patients in both the CVT-301 treatment group and the observational cohort will be managed with their standard PD treatment throughout the study; modification of the standard PD treatment is permissible, as outlined in this protocol.
Treatment Duration:	The planned treatment period will be 52 ±2 weeks. Each patient in the CVT-301 treatment group will self-administer up to 5 doses of inhaled study drug per day. The maximum planned screening period is approximately 5 weeks. A follow-up pulmonary evaluation will occur at 4 to 5 weeks after the treatment period ends.
Criteria for Evaluation:	Safety Pulmonary safety will be evaluated from assessments of lung

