Patients will complete the PD Diary for the 3 consecutive days prior to TV2, TV3, TV4, TV5, and TV6. Patients will complete the Inhaled Dosing Log every day during the 12-month treatment period. As described previously, patients will be contacted by the clinic staff 1 to 3 days after TV1 and 2 weeks (± 3 days) prior to each visit for TV2, TV3, TV4, TV5, and TV6.

They will bring the PD Diary, Inhaled Dosing Log, empty capsules, inhalers, and unused supplies to the each clinic visit. If the patient begins to run low on study supplies in between treatment visits, they should contact the site. Unused supplies can be re-dispensed to the patient at each clinic visit, in addition to a sufficient number of new study drug kits to supply the patient until his/her next visit. Note: Any open kit (even if partially unused) may not be re-dispensed.

10.3.4. Treatment Visit/Observational Visit 2 (1 month [4 weeks \pm 5 days] after TV/OV1)

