- The patient will remain in the clinic until they go into the OFF state. After confirmation of an OFF state (between 2 and 5 hours after the patient has taken his/her oral PD medication), record the time of the OFF state and then perform a pre-dose UPDRS Part 3 assessment. Under clinic staff supervision, patients will prepare and self-administer their entire dose of inhaled CVT-301. The dosing time is defined to be when the patient's OFF state is recognized by both the patient and investigator to be at a level similar to the investigator-confirmed severity experienced at SV1 and preferably between 2 and 5 hours after their prior oral PD medication. A new inhaler will be provided for this dose, and patients will use study drug from the supplies brought to the visit.
- Perform serial UPDRS Part 3 assessments at 10, 20, 30, and 60 minutes post-dose.
- Observe the patient for the appearance of dyskinesia and note in the eCRF if the patient experiences dyskinesia at any time within the 60-minute post-dose period. Also, if applicable, record the maximum severity of dyskinesia during the 60-minute post-dose period.
- Observe the patient for the occurrence of an ON state during the 60-minute post-dose period and note whether this occurs. If the patient converts to the ON state, note whether or not the patient is still in the ON state at 60 minutes post-dose.
- Monitor patients for AEs throughout the visit.

Once all of the assessments are complete, schedule the patient to undergo a DLco assessment 4 to 5 weeks after completion of TV6. The DLco assessment should be performed in an ON state (as reported by the patient to the pulmonary technician) in the pulmonary function facility. As part of the procedure, a slow vital capacity maneuver will be first, followed by DLco, and then spirometry.

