10.3.8.2. Observational Visit 6 / Early Withdrawal Visit for the Observational Cohort

Patients will report to the clinic after having taken their usual PD medications prior to the visit. The timing of administration of the usual morning dose of PD medication may be adjusted by the investigator to accommodate the patient's and/or clinic's schedule. Following their usual morning PD medication, no further PD medications will be used until following completion of all assessments. The timing of arrival should be scheduled to increase the likelihood that patients will be in an ON state upon arrival (i.e., they should arrive to the clinic as shortly as feasible after taking their standard oral PD medications at home). Patients will bring to the clinic all usual PD medications.

The following procedures will be done:

- Confirm that the DLco assessment was performed within 2 weeks prior to OV6. If the DLco assessment has not been completed prior to the visit, the study visit must be re-scheduled.
- Record any changes in the usual PD medication dose/regimen.
- Record any changes in concomitant medications.
- Perform the PDQ-39, UPDRS Part 2, and S&E ADL (each preferably in the ON state and must be before other study evaluations).
- Perform a brief physical examination.
- Record standard vital signs (BP, HR, and RR) and orthostatic vital signs (BP and HR).
- Perform 12-lead ECG.
- Perform spirometry assessment (preferably in the ON state; however, if the patient is not in an ON state, perform the evaluation and record the motor state with each assessment).
- The C-SSRS, Epworth Sleepiness Scale, and QUIP should be completed.
- Collect blood for clinical laboratory tests including serum pregnancy test, if applicable. Document fasting status.
- Monitor patients for AEs.

Once all of the assessments are complete, schedule the patient for a DLco assessment 4 to 5 weeks after OV6. The DLco assessment should be performed while the patient is in an ON state (as reported by the patient to the pulmonary technician) at the pulmonary function facility. As part of the procedure, a slow vital capacity will be performed, followed by DLco, and then spirometry.

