10.3.9. Early Withdrawal Visit

Patients in the CVT-301 treatment group who withdraw prematurely will complete the TV6 assessments for the CVT-301 patients (see [Section 10.3.8.1](#)), except for the pre-TV6 DLco assessment, at the time of withdrawal. Patients in the observational cohort who withdraw

prematurely will complete the OV6 assessments for the observational cohort (see [Section 10.3.8.2](#)), except for the pre- OV6 DLco assessment, at the time of withdrawal.

All patients who withdraw early, regardless of treatment group, will be scheduled to undergo a DLco assessment 4 to 5 weeks after completion of the Early Withdrawal Visit. The DLco assessment should be performed in an ON state (as reported by the patient to the pulmonary technician) in the pulmonary function facility. As part of the procedure, a slow vital capacity maneuver will be first, followed by DLco, and then spirometry.

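### SAEs are reportable for 4 weeks after treatment stops, but no site contact or assigned AE enquiry is scheduled after TV6/OV6 or early withdrawal, so new events are found only passively

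*Protocol*

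**What the plan says.** Section 11.1.9 sets a duty with two limbs: "An SAE occurring during the study or within 4 weeks of stopping the treatment must be reported to the" safety contact, whatever the cause. The deadline is "24 hours of occurrence or when the investigator becomes aware of the event".

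At TV6 (Section 10.3.8.1), under staff supervision, "patients will prepare and self-administer their entire dose of inhaled CVT-301". Once the assessments are complete, sites are to "schedule the patient to undergo a DLco assessment 4 to 5 weeks after completion of TV6". Section 10.3.8.2 gives the matching step for the observational cohort: "schedule the patient for a DLco assessment 4 to 5 weeks after OV6". Section 10.3.9 does the same for those who leave early: "All patients who withdraw early, regardless of treatment group, will be scheduled to undergo a DLco assessment 4 to 5 weeks after completion", with the interval there counted from the Early Withdrawal Visit. The Synopsis, under Treatment Duration, describes this appointment as pulmonary: "A follow-up pulmonary evaluation will occur at 4 to 5 weeks after the treatment period ends".

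For the CVT-301 group, Section 10.3.3 says that "patients will be contacted by the clinic staff 1 to 3 days after TV1 and 2 weeks" (±3 days) before each of TV2 to TV6. Section 10.3.1 gives the observational cohort calls 2 weeks before OV2 to OV6. Neither section lists a call after the final visit.

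**The concern.** The protocol creates a post-treatment reporting period but schedules no step by which the site would learn of a new event in it. The final test is done outside the clinic by facility technicians, and Section 11.1.7 sends the DLco data to a central reviewer. No section asks the technicians to enquire about adverse events or gives them a route for telling the site.

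This is a safety trial of an inhaled drug with pulmonary safety as its primary objective, so the weeks just after dosing stops deserve the same active enquiry as the weeks before. Context for the last lung test is also at stake. Before TV/OV1 the protocol checks by telephone that the patient has been free of respiratory infection for at least 3 days (Sections 9.4.1 and 10.3.1); no similar check precedes the final test. The ban on oral as-needed levodopa in the CVT-301 group also ends at TV6 (Section 9.4.2), as the inhaled drug stops. PD treatment may therefore change in an interval when no contact is scheduled to record it.

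**Working it through.** The plan gives no figure to reproduce. The check sets the reporting period against the contact schedule.

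**1. Reporting period.** For a CVT-301 completer the last scheduled dose is at TV6 (day 0). Four weeks is 4 × 7 = 28 days, so the post-treatment limb covers days 0 to 28.

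**2. Later appointment.** The DLco test falls at 4 to 5 weeks, that is days 28 to 35. Section 11.1.7 and the footnotes to Appendices 14 and 15 list its content as slow vital capacity, DLco and spirometry.

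**3. Scheduled site contacts with AE monitoring, from TV1/OV1 onward** (Sections 10.3.1 to 10.3.8):

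| | CVT-301 | Observational |
|---|---|---|
| Clinic visits 1 to 6 | 6 | 6 |
| Call 1 to 3 days after TV1 | 1 | 0 |
| Calls 2 weeks before visits 2 to 6 | 5 | 5 |
| Total up to and including visit 6 | 12 | 11 |
| After visit 6 | 0 | 0 |

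**4. Time and events tables.** Appendices 2 to 13 each have a telephone-contact column. Appendices 14 and 15 have a post-visit assessments column instead, and the DLco test is its only entry. In Section 10.3.8.1, AE monitoring is tied to the visit itself.

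**5. Extent of the interval without enquiry.** Per patient it is 4 to 5 weeks. Patient-time = n × weeks / 52, assuming every patient counted is followed for the whole interval:

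- All enrolled (Section 12.1, 250 + 115 = 365): 365 × 4/52 = 28.1 to 365 × 5/52 = 35.1 patient-years. The CVT-301 part is 250 × 4/52 = 19.2 to 250 × 5/52 = 24.0.
- Assumed completers (Section 12.1, 188 + 86 = 274): 274 × 4/52 = 21.1 to 274 × 5/52 = 26.3 patient-years. The CVT-301 part is 188 × 4/52 = 14.5 to 188 × 5/52 = 18.1.

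The first line is an upper bound. Some patients will be lost or will withdraw consent, and a patient who stopped the drug before the Early Withdrawal Visit has part of the 4 weeks covered by that visit.

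**The case against.** Several safeguards exist. Section 11.1.8 requires known events to be followed after therapy ends until they resolve or stabilise. Section 8.3 requires events that led to withdrawal to be followed, when possible, to resolution. Section 10.3.10 allows unscheduled visits. These stand, and they limit the point to new-onset events: follow-up of a known event does not find a new one, and an unscheduled visit needs something to prompt it.

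Section 11.1.8 also has patients asked about problems at every visit, and Appendices 14 and 15 call the last appointment a DLco visit. That is arguable, but the same section speaks of questioning by study staff, and nothing gives laboratory technicians the task.

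Three stronger readings are tempting and are not supported:

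- **That the reporting period closes before the lung test, or leaves the observational cohort out.** The first limb covers events during the study, and Section 7 lists the 4-to-5-week laboratory follow-up among the things the study includes. Read together, they can carry the duty to that test in both arms. Section 12.5 ends the observational cohort's TEAE period at OV6 or early withdrawal, so the end is ambiguous, but it is not an error.
- **That sites are given a duty they cannot meet.** The deadline includes investigator awareness, so a site that has not learned of an event is not thereby in breach. The issue is ascertainment.
- **That a number of missed SAEs can be stated.** The protocol gives no SAE rate and no basis for the share that would go unreported. Any rate applied to the patient-time would count events occurring, not events missed.

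It is also fair that the primary objective concerns 12 months of spirometry, and that no objective or Section 12 analysis depends specifically on the post-TV6 test.

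**Conclusion.** The gap is real. After TV6/OV6 or the Early Withdrawal Visit the protocol schedules no site contact and assigns no adverse-event enquiry, although SAEs remain reportable for at least 4 weeks after the drug stops. New-onset events in that interval are found only passively. The size is 4 to 5 weeks per patient, or at most 28 to 35 patient-years if all 365 enrolled patients are followed, of which 19 to 24 are in the CVT-301 group.

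The conclusion rests on the visit text, the call schedule and the appendices taken as complete, and on reading the each-visit question as a task for study staff. It does not affect the sample size or the 12-month spirometry analysis. It bears on the completeness of post-treatment safety data and, to a lesser degree, on the context for the last lung test.

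**What to change.** **Contact.** In Sections 10.3.1, 10.3.8 and 10.3.9 and Appendices 14 and 15, add one scripted site telephone call in both arms at the time of the 4-to-5-week DLco test. In the CVT-301 group it should come no earlier than 4 weeks after the last dose. The call asks about AEs, SAEs and medication changes, and is made even if the DLco test is missed.

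**Reporting period.** In Section 11.1.9, keep the existing limb of 4 weeks from stopping treatment, since it still works for a patient who stops the drug and never attends a final visit. Add that the during-study limb runs, in both arms, through the DLco test or call that follows TV/OV6 or early withdrawal. If neither takes place, it ends 5 weeks after TV/OV6 or early withdrawal.

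**Cost.** One call per patient, of a kind that sites already make before each visit, and a few more reported events to process. No dose, clinical rule or planned analysis changes.

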11.1.10. Suspected Unexpected Serious Adverse Reactions

Adverse events which meet all of the following criteria will be classified as suspected unexpected serious adverse reactions (SUSARs) and will be reported to the appropriate regulatory authorities in accordance with applicable regulatory requirements for expedited reporting:

- Serious
- Unexpected (i.e., is not consistent with the applicable product information such as the Investigator's Brochure for an unapproved investigational product or summary of product characteristics or product insert for an authorized product)
- There is at least a reasonable possibility that there is a causal relationship between the event and the medicinal product.

It is the Sponsor's responsibility to report SUSARs to the IRBs, IECs, and regulatory agencies in each country, although this responsibility may be delegated to the contract research organization (CRO). The procedures for notifying the health authorities and the IRBs/IECs of all SAEs/SUSARs (as appropriate) will be documented in the CRO study-specific and Sponsor standard operating procedure (SOP). SUSARs will be reported to the appropriate health authorities within 7 or 15 days (as appropriate).

11.1.11. Other Significant Adverse Events

To ensure patient safety, the investigator should also notify the medical monitor should any AE occur that is considered significant but does not meet criteria for an SAE, or that is considered unexpected. An unexpected AE is an AE that is not identified in nature, intensity, or frequency in the investigational drug brochure. The medical monitor and/or Sponsor may then choose to discontinue the patient from the study. In addition, any field monitor who notes a significant AE

or medical condition while reviewing the eCRFs or source documents at the site must immediately convey this information to the medical monitor.

11.1.12. Other Safety Assessments

11.1.12.1. UPDRS Part 4 (CVT-301 Treatment Group) and Examiner-Rated Dyskinesia

The UPDRS Part 4 is an assessment of potential complications of PD therapies. Questions 32-35 (related to dyskinesias) and 36-39 (related to clinical fluctuations) only will be completed for the CVT-301 patients as indicated in the time and events tables in [Appendix 2](#) through [Appendix 15](#).

Additionally, during the post-dosing follow-up period at TV/OV2, TV/OV3, TV/OV4, TV/OV5, and TV/OV6, observe the patient for the appearance of dyskinesia, and note in the eCRF if the patient experiences dyskinesia within the 60-minute post-dose period. If applicable, record the maximum severity of any dyskinesia during the 60-minute post-dose period. The examiner will also note if the patient converts to the ON state during the 60-minute post-dose period and if so, whether the patient is still in the ON state at 60 minutes post-dose.

